## Study summary

## Title

A randomised controlled pilot study to determine the effect of irrigation techniques used to enhance the release of endogenous signalling molecules from dentine matrix to treat apical periodontitis.

## Short Title

Therapeutic Irrigation Procedures to Treat Apical Periodontitis (TIPTAP)

## Study Design

Parallel group randomised controlled pilot study

## Objectives

1. Determine the clinical effect of using irrigation techniques to enhance the release of endogenous signalling molecules from dentine matrix in order to treat apical periodontitis.

2. Determine the change in profile of inflammatory markers as sampled from apical lesions during conventional non-surgical root canal treatment (NSRCT) and NSRCT using irrigation techniques to enhance the release of dentine Extracellular Matrix Components (dEMCs).

## **Population Studied**

Inclusion Criteria:

- Patients diagnosed with apical periodontitis
- Single rooted permanent teeth
- Medically fit
- Adult patients ( $\geq$  18)
- Voluntarily consent to partake in the study

#### Exclusion Criteria:

- Teeth in sextants with active periodontal disease (i.e. pocketing of  $\leq$  5 mm)
- Tooth unable to retain a rubber dam
- Teeth that have had previous endodontic treatment
- Root apex in close proximity to the maxillary sinus

- Patients who have had antimicrobial therapy within 3 months prior to the screening clinic
- Pregnant or breastfeeding women
- Do not have capacity to consent
- Patients that have systemic condition that would reduce immune function

## Sample Size

Up to 40 patients with apical periodontitis will be enrolled in this study across 2 groups

## Parallel Groups

**Group 1**: Two visit non-surgical root canal therapy (NSRCT) with conventional irrigation techniques (control arm) **Group 2**: Two visit NSRCT with irrigation protocol to optimise release of soluble dentine extracellular matrix components (dEMCs) (intervention arm)

## Planned Study Period

24 - 30 months. 12 - 18 months for recruitment and then another 12 months for follow up and data analysis.

## Funding and support in kind

| FUNDER(S)                  | FINANCIAL AND NON FINANCIAL SUPPORT GIVEN |
|----------------------------|---|
| British Endodontic Society | £20 000                                   |

## Role of study sponsor and funder

The University of Birmingham in the role of the sponsor will have oversight of the project. The funder, British Endodontic Society, will provide funding for the completion of the proposed study.

## **Protocol contributors**

The protocol has been created by the research team.

## Key Words

[figure not shown]
- Endodontics

- Dentine extracellular matrix components
- Growth factors
- Apical periodontitis
- Cytokines
- Periradicular tissue fluid
- Inflammation

## Patient Pathway

Participants diagnosed with apical periodontitis will be initially identified and made aware of the study by a member of their direct care team on a routine consultation clinic held at the Birmingham Dental Hospital. Patients who express interest in the project will be given a patient information sheet (PIS) and referred (via letter or secure email of a signed reply slip containing the patients contact information) to a research screening clinic held at the Birmingham Dental Hospital. Here, a GCP trained clinical member of the research team will discuss the study with the potential participant, answer any questions and confirm that they are eligible against the predetermined inclusion/exclusion criteria. Those who are eligible for inclusion will then be consented by the GCP trained research member and subsequently booked onto 2 treatment sessions where they will be randomly allocated to receive either standard care (NSRCT with conventional irrigation techniques), or experimental care (NSRCT with irrigation protocol to optimise release of soluble dEMCs). The 2 appointments will be approximately 14 days apart and the patient will have to attend a 12 month review appointment for assessment and once completed they exit the study. These timelines comply with the routine care pathway of patients receiving treatment for apical periodontitis at the Birmingham Dental Hospital and are consistent with ESE 2006 quality guidelines so will place no extra burden on them or the treatment site.

Study flow chart

Non-CTIMP Version number:

V 2.0

Version date: 11/06/2019

## Study Protocol

A randomised controlled pilot study to determine the effect of irrigation techniques used to enhance the release of endogenous signalling molecules from dentine matrix to treat apical periodontitis.

## Background

Apical periodontitis is a diagnostic term used to describe a localised inflammatory reaction caused by interactions between the host's immune response, and pathogenic bacterial communities within the root canal of an infected tooth (Kakehashi et al., 1965; Nair 1997). Its prevalence within the UK is documented to be between 4.1% and 5.8% however, in poorly root treated teeth, its occurrence is much higher with instances ranging from 38.3% to 47.4% (Di Fillipo et al., 2014, Dutta et al., 2014). At a molecular level this inflammatory process, which clinically results in bone resorption with mild to severe pain, is regulated by a myriad of pro and anti-inflammatory signalling molecules (Metzger et al., 2003). Collectively these mediators result in regulatory immune responses that serve destructive and protective functions which respectively possess the ability to control the progression of the inflammatory lesion or if favourable conditions exist, repair and regenerate healthy tissue architecture (Marton & Kiss, 2014). These molecular changes orchestrate the inflammatory process and precede any clinical symptoms (Marton & Kiss, 2014).

Current strategies for treating apical periodontitis focus exclusively on eliminating microorganisms entrenched within the root canal space. This is typically achieved via endodontic treatment where a combination of bactericidal irrigating solutions and mechanical instrumentation to disinfect the canal and reduce the microbial load (ESE 2006). Conventionally, sodium hypochlorite (NaOCI) has been the irrigant of choice, largely due to its ability to dissolve organic tissue and its efficacy against a broad range of microbiota (Haapasalo et al., 2010). Ethylenediaminetetraacetic acid (EDTA) is also commonly used in conjunction with NaOCI due to its ability to break down the inorganic tissue and debris that is produced from instrumenting the root canal (Gulabivala et al., 2005). The resultant disinfection alters the dynamic equilibrium between bacteria and host's immune components to favour the latter, which permits healing. Although the equipment available to chemically and mechanically disinfect the canal has improved radically in the last 20-30 years ([name] & Simon 2016), following such an ideology has only produced complete healing in 83% of cases when primary root canal treatment is undertaken and 80% of cases when teeth are retreated (Ng et al., 2011). This static nature of endodontic success rates over time has placed a significant burden on secondary care services as evidenced by rises in referrals (Al-Haboubi et al., 2014), extensive waiting lists and avoidable use of antimicrobials due to the difficulty of accessing such services (Segura-Egea et al., 2017).

For many years, it has been known that numerous bioactive molecules (dECMs), which are typically involved in wound healing processes such as proliferation and bone formation, are sequestered within the structure of the dentine (Smith et al., 2010). A commonly used chelating agent, EDTA irrigant solution, has been shown to release a complex cocktail of these soluble dEMCs (Graham et al., 2006, [name] et al., 2007, [name] et al., 2013). These liberated dECMs have gone onto show significant antibacterial properties in vitro (Smith et al., 2012) and the ability to induce the functional processes of dental tissue repair ([name] et al 2017). Therefore, the release of these naturally occurring signalling molecules during NSRCT could modulate the localised inflammatory process and potentially improve success rates for the treatment of apical periodontitis, a concept which has not yet been investigated. *In vitro* experiments conducted by our group have optimised irrigation protocols aimed at releasing dECMs which is different to conventional treatment so they are made bioavailable and can interact with inflamed periradicular issues during NSRCT. We hypothesise this intervention could potentially promote a reduction in inflammation, improve healing and lead to more favourable outcomes for patients suffering from apical periodontitis.

The primary aim of this study is to identify if any difference in clinical/radiographic signs of periradicular healing exist when control and intervention arms are compared that may suggest or otherwise that irrigation procedures aimed at enhancing the release of dEMCs improve treatment outcomes. Secondly, we aim to determine if the

adjunctive release of dEMCs during NSRCT modifies periradicular inflammatory mediator activity in comparison to that of conventional treatment, for teeth diagnosed with apical periodontitis. This study will not only help us to understand the process of healing following treatment of apical periodontitis at a molecular level, but also help us explore if there is therapeutic potential in enhancing dEMC release during root canal therapy to develop more biologically based treatment approaches to manage endodontic disease.

## Rationale

Our research group hypothesises that when compared to conventional NSRCT, the release of dEMCs will be associated with:

- i) An increased rate of clinical/radiographic periradicular healing
- ii) Modified inflammatory mediator activity

## Theoretical framework

The general aim of the proposed study is to evaluate the impact of clinical intervention which aims at enhancing the release of dEMCs during root canal treatment which is proposed may modulate the inflammatory process to enhance healing. Understanding how the signalling molecules released in soluble dEMCs interact with the periradicular inflammatory lesion at a molecular level could lead to the development of more biologically driven treatment strategies which improve success rates in patients suffering from periradicular disease. By studying the clinically relevant wound healing properties of specific endogenous dECMs, novel intracanal medicaments, irrigants and sealers could also be developed and be used as adjuncts to conventional root canal treatment. Furthermore, studying specific inflammatory mediators within the apical lesion will improve understanding of their role in the development and repair mechanisms of periradicular lesions and could inform future research on which periradicular cytokines to target as well as how to retrieve and analyse them.

## Research question/aims

1. Compared to routine care, does release of dEMCs from root dentine improve clinical outcomes of teeth with apical periodontitis?

2. Compared to routine care, does enhancing the release of dEMCs from root dentine modify the inflammatory process to promote healing of apical periodontitis?

## Objectives

The key objectives of this research are:

- Determine if NSRCT that adopts irrigation protocols to optimise release of soluble dEMCs (Compared to conventional irrigation protocols) can improve clinical outcomes in teeth with apical periodontitis.
- Establish a profile of key inflammatory mediators during active disease (prior to any significant intervention) and be able to compare the effects following conventional NSRCT (control arm) and NSRCT adopting irrigation protocols that optimise release of soluble dEMCs (intervention arm).

## Outcome

i) Primary Outcome:

- Success Rate

To analyse if the release of dECMs from the root canal improves the patient outcome following treatment the following clinical and radiographic parameters will be recorded prior to treatment, after one treatment intervention and after one year

- Clinical presence of pain (recorded using a visual analogue scale), swelling, sinus tract, pain on palpation, pain on percussion or mastication,
- Radiographic presence and size of lesion

Treatment success will then be determined based on criteria outlined by the European Society of Endodontology (ESE) Quality Guidelines for NSRCT (2006). In these criteria, outcomes are defined as being "favourable" (absence of pain, swelling and other symptoms, no sinus tract, no loss of function and radiological evidence of a complete healing), "uncertain" (absence of pain, swelling and other symptoms, no sinus tract, no loss of function and radiographic evidence of some healing) and finally "unfavourable" (tooth associated with clinical signs and symptoms of infection such as pain and swelling, sinus tract, loss of function and no radiographic evidence of healing). Comparisons in the success rate in the test and control groups will then be made to identify if there is any significant difference.

#### ii) Secondary Outcomes

- Determine profile of key inflammatory mediators in the presence of active disease and following treatment

To establish changes in the concentration of periradicular inflammatory mediators, periradicular tissue fluid (PTF) will be retrieved from the apical tissues associated with teeth at the start of and following NSRCT. This will be achieved by placing a paper point 2 mm beyond the end of the root canal for 60 seconds in a dry canal. The baseline sample will be taken on the first treatment visit prior to any intervention and then the second taken from the same tooth on the second treatment visit approximately 14 days later. The volume of extracted PTF will be determined using a wetted length to volume standard curve (Shimauchi et al., 1996). Once sampled, the PTF will be immersed in elution buffer and processed on clinic by vortexing for 60 seconds and then stored in a  $- 80^{\circ}$ C freezer at the Birmingham Dental School Research Lab. When ready to analyse, samples will be thawed at room temperature and the supernatant will undergo proteomic multiplex analysis to evaluate the concentration of a broad spectrum of inflammatory mediators, which will be represented in pg/ml. Through in vitro investigation our research group has optimised the sampling and elution procedure so that the maximum amount of PTF is absorbed onto the paper point, and the maximum amounts of analytes are recovered during elution.

## Study design and methods of data collection and data analysis

#### 5.1 Study Design

This pilot study has been designed as a parallel group randomised clinical trial design to compare the outcomes of standard care (NSRCT with a conventional irrigation technique) against the experimental intervention (NSRCT with an irrigation protocol to optimise release of soluble dEMCs). To generate preliminary data a total sample size of up to 40 participants, with up to 20 per group, will be required.

#### 5.1.1 Number of Participant

As the proposed analysis has not been previously reported, a power calculation to determine a statistically appropriate sample size cannot be performed. The proposed sample size (up to 40) is therefore based on previous studies which have analysed the changes in concentrations of various periradicular inflammatory mediators during NSRCT.

#### 5.1.2 Study Timeline

From the point of attaining ethical approval, the proposed research is expected to take 30-36 months to complete. The timeline (in months) of each individual stage is depicted in Figure 1.

Non-CTIMP Version number: V 2.0

Version date: 11/06/2019

|                               | Time Scale - Months |   |   |    |    |    |    |    |    |    |
|-------------------------------|---------------------|---|---|----|----|----|----|----|----|----|
|                               | 3                   | 6 | 9 | 12 | 15 | 18 | 21 | 24 | 27 | 30 |
| Pilot Study                   |                     |   |   |    |    |    |    |    |    |    |
| Patient Recruitment           |                     |   |   |    |    |    |    |    |    |    |
| Randomisation &
Allocation |                     |   |   |    |    |    |    |    |    |    |
| Delivery of Treatment         |                     |   |   |    |    |    |    |    |    |    |
| Molecular Analysis            |                     |   |   |    |    |    |    |    |    |    |
| 12 Month Review               |                     |   |   |    |    |    |    |    |    |    |
| Data Analysis                 |                     |   |   |    |    |    |    |    |    |    |
| Dissemination                 |                     |   |   |    |    |    |    |    |    |    |

Fig. 1 – Planned time scale for each stage of the proposed research project

#### 5.1.3 Study Procedures

All suitable participants that have volunteered to take part in this study will undergo 2 visits for NSRCT, each appointment being approximately 14 days apart. The treatment of patients in both groups follows conventional treatment protocols apart from the irrigant regime used to optimise release of dEMCs. Briefly on the first visit, the tooth will be anaesthetised with local anaesthetic and isolated with a rubber dam. Using cooled diamond burs, the root canal will then be accessed and shaped using rotary nickel-titanium files after the root length has been determined using an electronic apex locator in conjunction with a radiograph. In the control group, a conventional irrigant regime which does not release dentine matrix growth factors will be used whereas in the test group, a novel regime which has been optimised by our group to release dEMCs will be employed. The irrigants used in both groups are widely used solutions in endodontic therapy (Haapasalo et al., 2010) however, it is the timings at which these irrigants are used during root canal therapy which will allow the release of dentine matrix growth factors. Once these stages have been completed, a temporary filling will be placed onto the tooth and the patient recalled for the second visit approximately 14 days later. On the second visit, the temporary filling will be removed and the after the root canal filled followed by a permanent restoration to prevent bacterial ingress.

#### 5.1.4 Blinding

All irrigants used are clear fluids and are administered into the root canal using the same method. Therefore the operators (who will carry out the treatment) will be blinded to the irrigants being used during the experiment. The assessors (who will look at the results) will also be blinded once the data has been collected. In the case of a adverse event (i.e. inter-appointment flare up) the patient will be unblinded and the appropriate treatment provided.

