## 5.1.5 Randomisation & Allocation

A third party provider "Sealed Envelope", which provides its services free to PhD students, will be used to provide a web based randomisation service with a telephone as back up. Once eligibility criteria have been confirmed, consent is obtained and stratification variables determined through clinical/radiographic examination, the

Non-CTIMP Version number: V 2.0

Version date: 11/06/2019

randomisation can be performed. The allocation of participants into either control arm or intervention arm will be concealed to the operator until all outcome measures have been collected.

To ensure the test and control groups are matched and chance imbalances are avoided in important stratification variables, a computer based "minimisation" algorithm will be used. The variables chosen are:

- Age (18 30 / 31 50 / > 51)
- Gender
- Ethnicity
- Size of apical lesion (1 5 mm / > 6 mm)

The procedures for randomisation will be fully documented and piloted prior to the start of the trial.

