## Safety reporting

## Adverse Events

All medical occurrences, including any unexpected out of range laboratory values, which meet the definition of an AE will be reported on an AE form.

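### The automatic code break after an inter-appointment flare-up (5.1.4) is not reconciled with concealment until all outcomes are collected (5.1.5), and can unmask later clinical assessments in a subset selected by symptoms

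*Protocol*

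**What the plan says.** Section 5.1.4 (Blinding) contains three statements that matter here.

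- On operators: "Therefore the operators (who will carry out the treatment) will be blinded to the irrigants being used during the experiment".
- On assessors: "The assessors (who will look at the results) will also be blinded once the data has been collected".
- On adverse events: "In the case of a adverse event (i.e. inter-appointment flare up) the patient will be unblinded and the appropriate treatment provided".

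Section 5.1.5 (Randomisation & Allocation) then says: "The allocation of participants into either control arm or intervention arm will be concealed to the operator until all outcome measures have been collected". It names no exception for adverse events or for any other reason.

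The Outcome section lists the clinical components of the primary outcome: "Clinical presence of pain (recorded using a visual analogue scale), swelling, sinus tract, pain on palpation, pain on percussion or mastication". Together with lesion presence and size, these "will be recorded prior to treatment, after one treatment intervention and after one year". The section on roles and responsibilities gives the chief investigator, the PhD student and one co-investigator both the delivery of treatment and the collection of follow-up clinical and radiographic data. Section 5.2 (Data Collection) assigns the pre-operative and 12-month case report form data to the chief or principal investigator.

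**The concern.** The code-break rule sets no test of whether knowing the arm is needed to look after the patient. Its trigger is a symptomatic event between the two treatment visits, before most of the outcome data exist. The symptoms of such an event overlap with the signs that later decide clinical success. The patients whose allocation becomes known are thus not a random subset: they are picked out by symptoms of the kind being measured.

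The Background hypothesises that the intervention reduces inflammation, so the frequency of flare-ups could differ between arms. If it does, unmasking would be related to arm as well as to prognosis. The protocol supports this only as a possibility.

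At stake is whether the self-reported pain score and the examiner's findings on swelling and tenderness are masked in these patients. There is also a practical problem: if the treating clinician is told the arm, staff facing a flare-up cannot follow both sections as written.

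**Working it through.** There is no plan figure to reproduce. Section 5.1.1 says that no power calculation can be performed, and the protocol gives no flare-up or adverse event rate. The check is mainly a comparison of the text.

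**Step 1: the two rules.** Section 5.1.4 requires unblinding on the named event. Section 5.1.5 requires concealment from the operator until every outcome has been collected. Neither refers to the other.

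**Step 2: who learns the arm.** Section 5.1.4 speaks of the patient, section 5.1.5 of the operator. The link between them is that 5.1.4 joins unblinding to the provision of treatment, which has little purpose unless the treating clinician is told. In addition, 5.1.4 describes only operators and assessors as blinded, so unblinding the patient most naturally means breaking that patient's code. If only the patient were told, the later pain score on the visual analogue scale would still be reported unmasked.

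**Step 3: timing.**

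| Event or measurement | When | Source |
|---|---|---|
| Baseline signs and fluid sample | before or at visit 1 | Outcome; 5.2 |
| Inter-appointment flare-up | between visits 1 and 2, about 14 days apart | 5.1.3; 5.1.4 |
| Second fluid sample | visit 2 | Secondary Outcomes; 5.2 |
| Clinical signs after one treatment | after visit 1 (Outcome section only; 5.2 does not list it) | Outcome |
| Primary outcome | 12 months | Outcome Measures; Outcome |

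The trigger precedes the second fluid sample, any visit-2 clinical recording and the 12-month classification.

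**Step 4: who records the later data.** The roles section lets the people who treat also collect follow-up data, and 5.2 names the chief or principal investigator for the 12-month form. The only stated masking of assessors begins after the data have been collected. Nothing stated therefore protects the 12-month examination of a patient whose code has been broken.

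**Step 5: which outcomes are exposed.** A favourable result requires both absence of symptoms and complete radiographic healing. The clinical half is patient-reported or examiner-judged, so it is open to influence. Lesion size is to be measured on CBCT (Assessment and management of risk), and mediator concentration comes from a multiplex assay. Both are much less exposed.

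**Step 6: scale, illustration only.** Inputs: N = 40, the maximum in 5.1, and an assumed flare-up rate p. Expected number unblinded = 40 × p. Chance of at least one = 1 − (1 − p)^40.

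| Assumed p | Expected number | Chance of at least one |
|---|---|---|
| 2% | 40 × 0.02 = 0.8 | 55% |
| 5% | 40 × 0.05 = 2 | 87% |
| 10% | 40 × 0.10 = 4 | 98.5% |
| 20% | 40 × 0.20 = 8 | >99.9% |

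With 20 patients in an arm, one patient classified differently moves that arm's success rate by 1/20 = 5 percentage points. This applies only if unmasking actually changes the classification, and the protocol gives no basis for saying how often it would.

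**The case against.** The strongest reply is that 5.1.5 is a general rule, 5.1.4 is a specific safety exception, and only a cross-reference is missing. Literally, the two sections also address different people, the patient and the operator. This stands in part. The conflict rests on a strong implication about who is told, not on explicit words, and code-breaking for safety is not an error in itself. But the reply does not explain why the break must be automatic, and it leaves unstated who is told and whether the later assessor remains masked.

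A reader might also infer several stronger points that the protocol does not support:

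- *Every adverse event breaks the blind.* The parenthesis in 5.1.4 literally confines the trigger to inter-appointment flare-ups. The protocol sometimes uses that abbreviation loosely, so the wording is at most ambiguous.
- *The Adverse Events section widens the trigger.* Its sentence, "All medical occurrences, including any unexpected out of range laboratory values, which meet the definition of an AE will be reported on an AE form", is a reporting rule. It does not itself define an adverse event and says nothing about unblinding.
- *Both the primary and the secondary comparisons are biased.* The assay result is neither a patient's report nor an examiner's judgement, and the radiographic part of success is measured on CBCT. Visit-2 pain scores do not enter the 12-month classification as the Study summary describes it.
- *Each unmasked patient costs 5 points.* That holds only for a patient whose classification changes.

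**Conclusion.** The point holds in a limited form. The protocol fixes an unconditional code break, triggered by a symptomatic event that precedes the visit-2 recordings and the 12-month outcome, and leaves it unreconciled with its own concealment rule. As treating investigators may collect follow-up data, the later pain score and examiner-judged signs of these patients may be recorded with the allocation known.

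This rests on two assumptions: that the treating clinician is told the arm (or at least that the patient is, which affects the pain score), and that someone who was told may carry out the later assessment. Both fit the text, but neither is stated outright.

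The number affected and the size and direction of any bias cannot be computed from the protocol. The table above shows only that, even at an assumed rate of 2%, at least one such code break is more likely than not if 40 patients are enrolled. The correction is worth making because a stated rule creates an avoidable risk of bias and is cheap to change.

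**What to change.** Amend 5.1.4 and 5.1.5 together.

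1. Replace the automatic rule in 5.1.4. The code is broken only when the treating clinician records that knowing the allocation is needed to manage the event.
2. State this in 5.1.5 as the exception to concealment.
3. Log each code break with its date, the reason and who was told.
4. Have that participant's 12-month assessment done by an existing team member who has not been told the allocation. Adjust 5.2 so that its named data collector does not prevent this; the roles section already gives three people follow-up data collection.

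How the event is treated is left to the clinicians and is not at issue here. The cost is about one paragraph of amendment, a code-break log and some scheduling of existing assessors.
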